# 4.1 Study Endpoints

## 4.1.1 **Primary Endpoint**

The primary endpoint is duration of sustained **islet allograft function** as determined by evidence from MMTT of c-peptide production at each anniversary of the final transplant. A c-peptide level greater than or equal to 0.3 ng/mL at 0, 60, or 90 minutes will be considered evidence of islet allograft function.

## 4.1.2 Secondary Endpoints

Secondary endpoints include the following:

- Serum creatinine and calculated eGFR at each annual study visit
- Incidence of serious adverse events during the 12-month period preceding each annual study visit
- Insulin requirements during a one-week period preceding each annual study visit
- Incidence of severe hypoglycemic events during the 12-month period preceding each annual study visit
- HbA1c levels at each annual study visit
- All causes of mortality
- Presence of alloantibody after graft failure, in the absence of immunosuppression

## 5. STUDY TREATMENT REGIMEN

## 5.1 Immunosuppression Medications

The marketed immunosuppressive medications in this protocol will be obtained by prescription unless provided by the study through the drug distributor. Generic brands are allowed, when available.

## 5.1.1 Drug Accountability

Under Title 21 of the Code of Federal Regulations (21CFR §312.62), the investigator is required to maintain adequate records of the disposition of immunosuppressants provided for the study through the drug distributor, including the date and quantity of the drug received, to whom the drug was dispensed (subject-by-subject accounting), and a detailed accounting of any drug accidentally or deliberately destroyed.

Records for receipt, storage, use, and disposition will be maintained by the study site. A drugdispensing log will be kept current for each subject. This log will contain the identification of each subject and the date and quantity of drug dispensed.

All records regarding the disposition of the study-provided immunosuppressants will be available for inspection by the clinical trial monitor.

## 5.2 Concomitant Medications

Antibacterial, antifungal, and antiviral prophylaxis, insulin therapy, and other standard therapies will be provided per site-specific practices. The cost of these drugs will not be covered under this protocol. Substitution of non-brand name generic equivalents for those protocol required medicines is permitted to reduce cost to the patients and/or their insurance companies.

## 5.3 Rescue Medications

Rescue therapy will not be initiated in this protocol to treat suspected rejection. Immunologic surveillance methods that would allow diagnosis of islet allograft rejection early enough for timely intervention have yet to be identified and validated.

## 5.4 Prohibited Medications

None.

## 6. Criteria for Premature Termination of the Study

# 6.1 Subject Withdrawal Criteria

Subjects may be prematurely terminated from study for the following reasons:

- 1. The subject elects to withdraw consent from all future study activities, including follow-up.
- 2. The subject is "lost to follow-up" (*i.e.*, no further follow-up is possible because attempts to reestablish contact with the subject have failed).
- The subject dies.
- 4. The investigator determines that it is not in the subject's best interest to continue.
- 5. The subject enrolls and begins study treatment in another investigational protocol for islet transplantation while enrolled in this study.

Subjects who prematurely terminate from this study will not be replaced. If possible, assessment of adverse events will be collected prior to termination (see section 8). Data from such subjects obtained before withdrawal of consent or before being lost to follow-up will be used in the intent-to-treat analysis. If a subject with functioning transplanted islets chooses to withdraw from the protocol, s/he will be informed of their risk for losing his/her islet graft and becoming sensitized if s/he chooses to discontinue immunosuppressive therapy and return to his/her original method of insulin management.

# 6.2 Subject Stopping Rules

#### 6.2.1 Subject Stopping Rules

None.

## 6.2.2 Study Stopping Rules

None.

## 7. STUDY PROCEDURES

## 7.1 Enrollment and Screening

Patients who meet the general inclusion criteria for this study will be approached regarding their participation in this study. The study procedures, risks, and potential benefits will be discussed with the potential study subject in lay language. The potential study subject will have an opportunity to review the informed consent and ask questions.

Once informed consent has been obtained, the subject will be enrolled. Subject eligibility will be confirmed through information collected from their most recent CIT study visit. If more than 90 days have elapsed since the subject's last CIT study visit, then the screening visit assessments should be performed in order to confirm eligibility.

# 7.2 Follow-up Visits

Subjects will be followed in this study after termination from the CIT parent study until the end date of the CIT08 study. Follow-up is comprised of quarterly visits done locally for safety monitoring and annual visits at the study center to assess graft function (if applicable) and safety.

Retrospective medical chart review will be conducted as needed to collect available follow-up information due to:

- delayed enrollment in CIT08 after termination from the CIT parent study
- the time period between termination from CIT08 prior to extension of the duration of follow-up and subsequent re-enrollment

This retrospective chart review will collect evidence of graft failure in addition to the follow-up assessments outlined in Appendix 1.

Subjects are allowed to concurrently enroll in and be screened for a non-CIT islet transplant study at any point during participation. Once study treatment in the non-CIT study is initiated, they will be withdrawn from CIT08 (see section 6.1).

Subjects with confirmed **graft failure** will not complete metabolic assessments. Subjects who experience graft failure and subsequently stop immunosuppression will have alloantibody assessed 3 months after their last dose of immunosuppression.

#### 7.3 Visit Windows

If the screening visit occurs within 90 days of the subject's final parent study visit, the results from the final parent study visit should be used. If the screening visit occurs more than 90 days after the final parent study visit, then the screening assessments must be repeated. Annual study visits will occur within plus or minus 30 days of the anniversary of the subjects' last parent study visit. Quarterly local visits will occur within plus or minus 14 days.

## 8. SAFETY MONITORING

## 8.1 Overview

This section defines the types of AEs and outlines the procedures for appropriately collecting, grading, recording, and reporting them. Information in this section complies with 21CFR 312; ICH Guideline E2A: Clinical Safety Data Management: Definitions and Standards for Expedited Reporting; and ICH Guideline E-6: Guidelines for Good Clinical Practice; and applies the standards set forth in the CIT Common Terminology Criteria for Adverse Events.

The investigator is responsible for the detection and documentation of events meeting the criteria and definition of an AE or SAE as described in section 8.2 of this protocol. AEs and SAEs will be recorded in the source documents and on the appropriate electronic CRF(s). All data will be reviewed periodically by the independent study monitor, who may provide recommendations to NIAID about withdrawing any participant and/or terminating the study because of safety concerns.

## 8.2 Definitions

## 8.2.1 Adverse Event

An adverse event (AE) is defined as any untoward or unfavorable medical occurrence associated with the subject's participation in the research, whether or not considered related to the subject's participation in the research (ICH E-6 Guidelines for GCP).

For this study, an adverse event will include any untoward or unfavorable medical occurrence associated with the following.

- Study therapy:
  - o None
- Study mandated procedures:
  - o Blood draws Any AE occurring within 24 hours after a protocol mandated blood draw.
  - o Metabolic testing Any AE occurring within 24 hours after study-required metabolic testing.

Adverse events occurring outside the designated time parameters should also be reported if the investigator deems a possible association with a study mandated procedure.

Recording of adverse events in this trial will be limited to:

- cirrhosis
- renal insufficiency
- malignancy
- hypoglycemia
- all adverse events meeting the serious criteria outlined in section 8.2.4.

## 8.2.2 Suspected Adverse Reaction (SAR)

A suspected adverse reaction (SAR) is any adverse event for which there is a reasonable possibility that the investigational study therapy or procedure caused the adverse event. For the purposes of safety reporting, 'reasonable possibility' means there is evidence to suggest a causal relationship between the study therapy or procedure and the adverse event. A suspected adverse reaction implies a lesser degree of certainty about causality than adverse reaction, which means any adverse event caused by a study therapy or procedure (21 CFR 312.32(a)).

#### 8.2.3 Unexpected Adverse Event

An adverse event or suspected adverse reaction is considered "unexpected" if it is not consistent with the risk information described in the protocol or other experience pertaining to study procedures in this population.

## 8.2.4 Serious Adverse Event

An adverse event or suspected adverse reaction is considered "serious" if, in the view of either the investigator or DAIT/NIAID, it results in any of the following outcomes (21CFR312.32(a)):

- 1) Death.
- 2) A life-threatening event. An AE or SAR is considered "life-threatening" if, in the view of either the investigator or DAIT/NIAID, its occurrence places the subject at immediate risk of death. It does not include an AE or SAR that, had it occurred in a more severe form, might have caused death.
- 3) Inpatient hospitalization greater than 24 hours or prolongation of existing hospitalization.
- 4) Persistent or significant incapacity or substantial disruption of the ability to conduct normal life functions.
- 5) Congenital anomaly or birth defect.
- 6) An event that required intervention to prevent permanent impairment or damage.
- 7) An important medical event that may not result in death, be life threatening, or require hospitalization may be considered an SAE when, based on appropriate medical judgment, it may jeopardize the participant and may require medical or surgical intervention to prevent one of the outcomes listed above.

# 8.3 Grading and Attribution of Adverse Events

## 8.3.1 **Grading Criteria**

The study site will grade the severity of AEs experienced by CIT study subjects according to the criteria set forth in the *CIT-TCAE*. This document provides a common language to describe levels of severity, to analyze and interpret data, and to articulate the clinical significance of all AEs.

AE severity will be graded on a scale from 1 to 5 according to the following standards in the *CIT-TCAE* manual:

Grade 1 = Mild AE.

Grade 2 = Moderate AE.

Grade 3 = Severe and undesirable AE.

Grade 4 = Life-threatening or disabling AE.

Grade 5 = Death.

Table 4: General severity definition of adverse event

Grade 1	Mild	Transient or mild discomforts (< 48 hours), no or minimal medical intervention/therapy required, hospitalization not necessary (non-prescription or single-use prescription therapy may be				
		employed to relieve symptoms, e.g. , aspirin for simple headache, acetaminophen for post-surgical pain).				
Grade 2	Moderate	Mild to moderate limitation in activity some assistance may be needed; no or minimal intervention/therapy required,				
		hospitalization possible.				
Grade 3	Severe	Marked limitation in activity, some assistance usually required;				
		medical intervention/therapy required hospitalization possible.				
Grade 4	Life-	Extreme limitation in activity, significant assistance required;				
	threatening	significant medical/therapy intervention required hospitalization				
		or hospice care probable.				
Grade 5	Death	Death.				

AEs, not included in the CIT-TCAE listing, should be recorded and their severity graded from 1 to 5 according to the General Grade Definition provided above.

All AEs will be reported and graded, by the PI or designee, whether they are or are not related to disease progression or study protocol.

#### 8.3.2 **Definition of Attribution**

Attribution will only be determined and collected for serious adverse events.

The relatedness, or attribution, of an SAE to a study procedure will be determined by the site investigator. The site investigator will also record the determination of attribution on the appropriate eCRF and/or SAE report form. The relationship of an SAE (attribution of SAE) to a study procedure will be defined by using the descriptors provided below.

Table 5: Attribution of adverse events

Code	Descriptor	Definition				
UNRELATED CATEGORY						
1	Unrelated	The adverse event is definitely not related to the study treatment.				
RELATED CATEGORIES						
2	Possible	The adverse event might or might not be related to the study treatment.				
		(This grade is assigned when uncertainty exists)				
3	Definite	The adverse event is definitely related to the study treatment.				

For additional information and a printable version of the CIT-TCAE manual, consult the CIT website: http://isletstudy.org.

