# 2. OBJECTIVES

# 2.1 Primary Objective

The primary objective is to provide extended follow-up for safety and efficacy and to support continued islet graft function to participants previously enrolled in CIT02, CIT03, CIT04, CIT05, CIT06, or CIT07.

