## 4. STUDY DESIGN

This is an open-label, multi-center cohort study for participants from the CIT02, CIT03, CIT04, CIT05, CIT06, and CIT07 studies who continue to have islet graft function. These participants will continue immunosuppressive medications under CIT08 and will be assessed for islet function on an annual basis.

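### CIT08 contradicts itself on what serious adverse events are attributed to, leaving no clear route to record relatedness to the continued immunosuppression

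*Protocol*

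**What the plan says.** All sections here are in the CIT08 extension protocol unless marked CIT-05.

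- **Exposure.** Section 4 says of subjects with graft function: "These participants will continue immunosuppressive medications under CIT08 and will be assessed for islet function on an annual basis". Section 5, headed as the study treatment regimen, concerns these drugs: "The marketed immunosuppressive medications in this protocol will be obtained by prescription unless provided by the study through the drug distributor". Section 5.1.1 adds accountability records for study-supplied drug.
- **Objective.** Section 2.1 aims to "provide extended follow-up for safety and efficacy and to support continued islet graft function".
- **Adverse event definition.** Section 8.2.1 begins "For this study, an adverse event will include any untoward or unfavorable medical occurrence associated with the following". It then enters None for study therapy and lists blood draws and metabolic testing as the mandated procedures. It limits recording to cirrhosis, renal insufficiency, malignancy, hypoglycemia and all SAEs.
- **Suspected adverse reaction.** Section 8.2.2 refers to a therapy or a procedure as the possible cause.
- **Attribution.** The text of section 8.3.2 reads "The relatedness, or attribution, of an SAE to a study procedure will be determined by the site investigator". Table 5 beneath it defines its middle code as "The adverse event might or might not be related to the study treatment", and its other two codes also refer to treatment.
- **Recording.** Section 8.4.3 has events recorded whatever their relation to a study procedure, and mentions no treatment.

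**The concern.** Immunosuppression is the main continuing hazard in CIT08. Section 1.4 describes infection, lymphoma and other malignancy, nephrotoxicity and progressive multifocal leukoencephalopathy as risks of these agents. Three of the event types singled out for recording (cirrhosis, renal insufficiency and malignancy) are not credible consequences of a blood draw or a meal test. The plan thus collects events suited to drug or transplant toxicity, while its attribution wording mostly asks about something else.

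What is at stake is whether the relatedness field can be interpreted. CIT08 has a single arm and no comparator for SAE incidence, so investigator attribution is the planned item that asks about cause. It is entered by the site on the case report form. A statistical analysis plan cannot later recover an answer to a question that was not asked, or was asked ambiguously.

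**Working it through.** The documents tie no sample size, error rate or threshold to CIT08 safety attribution, so there is no figure to reproduce. The check compares the sections.

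| CIT08 section | Exposure named |
|---|---|
| 5 and 5.1 | Immunosuppressants, as the treatment regimen |
| 8.2.1 | Therapy: None; procedures: blood draws and metabolic tests |
| 8.2.2 | Therapy or procedure |
| 8.3.2, text | Study procedure |
| 8.3.2, Table 5 (all three codes) | Study treatment |
| 8.4.3 | Study procedure |

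Take a lymphoma in a subject on continued immunosuppression, outside any link to a blood draw or metabolic test. Three readings are open to the site:

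1. **Text of 8.3.2.** The question is relatedness to a procedure. The answer is code 1, unrelated.
2. **Table 5 read with section 5.** The treatment is the immunosuppression. The answer is code 2 (possible) or code 3 (definite).
3. **Table 5 read with 8.2.1.** There is no study therapy to which the event could relate. The answer is code 1.

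Readings 1 and 3 put the event in the unrelated category, and reading 2 puts it in a related one. Each follows something the protocol says. The protocol does not ask the site to state which reading it used, so the code alone does not show which exposure was judged. A count of related SAEs pooled across sites would mix relatedness to procedures with relatedness to drugs in unknown proportion.

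The parent protocol avoids this. CIT-05 section 8.2.4.2 names the exposures to be judged: islet transplantation (product or procedure), rituximab, and immunosuppression or infection prophylaxis. A CIT-05 subject who moves into CIT08 goes from a protocol that names immunosuppression as an attribution target to one that does not clearly do so. Relatedness therefore cannot be followed across the two periods on the same basis.

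**The case against.** The strongest case on the other side has four parts.

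- **Safety review does not depend on attribution.** A reader might infer that immunosuppressant toxicity cannot trigger a review. The documents contradict that. Section 8.4.4.1 requires every SAE to reach the sponsor within 24 hours whatever its relationship. Under 8.5.1 the Medical Monitor triages SAE reports, and monthly cumulative reports are sent. Under 8.5.2 the DSMB sees all reported events yearly. Section 8.1 lets an independent monitor recommend termination, and section 11.1 lets the DSMB or IRB order it. This stands in full.
- **The absence of stopping rules is defensible.** Sections 6.2.1 and 6.2.2 read None. CIT08 is an IND-exempt follow-up of subjects already transplanted, using marketed drugs. Stopping the study would not by itself end exposure to prescribed drugs, but it would end the follow-up. Section 6.1 still allows an investigator to withdraw a subject. This also stands, and the point makes no claim against it.
- **Relatedness to immunosuppression may still be recorded.** A reader might infer that it is captured for no SAE at all. Table 5 and section 8.2.2 leave room for a site to code it, and the form itself is not shown. The documents support ambiguity, not total loss.
- **No stated result uses attribution.** Section 10.1.2 tabulates SAEs by body system and coded term. Creatinine, estimated GFR, SAE incidence and mortality are endpoints in their own right. This is correct, so no planned CIT08 estimate is biased. It does not remove the defect: the attribution data are collected, and any use of them in judging the safety of continued immunosuppression would rest on an undefined question.

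**Conclusion.** The point holds as an internal contradiction. Sections 5, 8.2.1, 8.2.2, 8.3.2 (text against Table 5) and 8.4.3 do not agree on the exposure to which an SAE is attributed. Followed as written, they let sites code the same event differently and give no clear route to record relatedness to the continued drugs.

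Its reach is every SAE in the approximately 75 subjects expected. Its numerical effect cannot be given, because the documents state neither an SAE rate nor how sites would divide between the readings. The conclusion assumes that the case report form follows section 8.3.2. If the form already asks about immunosuppression separately, the defect is confined to the protocol text.

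Event capture, expedited reporting and oversight are intact. The CIT-05 primary analysis, its attribution scheme and its stopping rules are not affected. The correction is worth making because safety is part of the CIT08 primary objective.

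**What to change.** 1. State once, in section 8.3.2, which exposures attribution refers to, and bring sections 5, 8.2.1, 8.2.2 and 8.4.3 into line with it.
2. In section 8.3.2 and Table 5, record two separate attributions for each SAE: one to immunosuppression and one to study procedures. This follows the parent protocol's practice of judging named exposures separately. The three existing codes can be kept for both.
3. In section 10.1.2, report SAE incidence by each attribution alongside the planned tabulation.
4. For SAEs already entered under the present wording, say whether the second item was completed retrospectively.

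No stopping threshold or DSMB trigger is proposed; whether one is wanted is for the sponsor and the DSMB.

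The cost is one extra item on an existing SAE form, wording changes in the sections named, and the amendment approvals required by section 13.1. No new visits, samples or committees are needed.

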## 8.4 Collecting and Recording of Adverse Events

## 8.4.1 Collection Period

AEs will be followed until resolution, stabilization, or until 30 days after a participant terminates from the study, whichever comes first.

## 8.4.2 Collecting Adverse Events

Adverse Events (including SAEs) may be discovered through any of these methods:

- Observing the subject.
- Receiving an unsolicited complaint from the subject.
- During their annual study visits and/or at the time of premature withdrawal from the study, subjects will be asked whether, in the past year:
  - They were hospitalized;
  - They had a medical issue requiring a visit to the emergency room or an urgent care clinic;
  - o They experienced any severe hypoglycemic events;
  - They have been diagnosed with a malignancy; and
  - o They have become pregnant or have plans for pregnancy.
- In addition, an abnormal value or result from a clinical or laboratory evaluation can also indicate an adverse event, as defined in Section 8.3, Grading and Attribution of Adverse Events.

#### 8.4.3 Recording Adverse Events

The investigator will record adverse events and serious adverse events as described previously (Section 8.2, Definitions) on the appropriate case report form regardless of the relationship to study procedure.

Adverse events must be recorded by the site on the appropriate AE/SAE CRF within 5 business days of awareness.

Adverse events collected on a case report form.

Once recorded, an AE/SAE will be followed until it resolves with or without sequelae, or until the end of study participation, or until 30 days after the subject prematurely withdraws (without withdrawing consent)/or is withdrawn from the study, whichever occurs first.

